4.7 Data Collection

The data collected will not be used for clinical diagnosis or treatment purposes. The data collected will be kept on a password secured UTMB computer. An encrypted USB flash drive will be used to transfer data. The data will be linked to the patient only by the patient's MRN number. This identifier will be needed to access and analyze demographic data. During analysis of the data, all identifiers will be deleted. Data will be collected from the patient's chart and the chart of the neonate. The data collected will include demographics and data needed to assess the primary and secondary outcomes listed below. The data collection sheet is uploaded for review by the IRB. It is imperative that studies involving induction and augmentation of labor and intrapartum care assess the outcomes of the neonate.

Study Summary Flow Diagram

4.8 Primary Outcome

- Length of induction to delivery interval

4.9 Secondary Outcomes

- Rate of primary cesarean delivery
- Mode of delivery (including operative vaginal delivery)
- Maximum dose of oxytocin infusion
- Uterine tachysystole without fetal heart rate (FHR) changes

- Uterine tachysystole with FHR changes
- Uterine tachysystole requiring cessation of oxytocin
- Incidence of postpartum hemorrhage
- Incidence of placental abruption
- Maternal side effects (including nausea/vomiting requiring antiemetics, diarrhea)
- Chorioamnionitis ("IAI" or "triple I")
 - o A presumptive diagnosis can be made in women with:
 - Fever $\geq 39.0^{\circ}\text{C}$ (102.2°F) one time or 38.0°C (100.4°F) to 38.9°C (102.02°F) on two occasions 30 minutes apart, without another clear source, PLUS one of the following:
 - Baseline fetal heart rate >160 beats/min for ≥ 10 minutes, excluding accelerations, decelerations, and periods of marked variability
 - Maternal white cell count $>15,000 \text{ mm}^3$ in the absence of corticosteroids and ideally showing a left shift (bandemia)
 - Purulent-appearing fluid coming from the cervical os visualized by speculum examination
 - o A confirmed diagnosis of chorioamnionitis can be made in women with:
 - All the above plus one or more of the following objective laboratory findings:
 - Positive Gram stain of amniotic fluid
 - Low glucose level in amniotic fluid
 - Positive amniotic fluid culture
 - High white cell count in amniotic fluid in the absence of a blood tap
 - Histopathologic evidence of infection or inflammation or both in the placenta, fetal membranes, or umbilical cord vessels (funisitis)
- Endometritis: must meet the following criteria:
 - o Infection occurs within 30 days after the operative procedure AND
 - o Infection presumed to involve the uterus AND
 - o Patient has at least one of the following:
 - Purulent drainage from a drain that is placed through a stab wound into the abdomen or pelvis
 - Organisms isolated from an aseptically obtained culture of fluid or tissue in the organ/space
 - An abscess or other evidence of infection involving the abdomen or pelvis that is found on direct examination, during re-operative, or by histopathologic examination
- Serious maternal morbidity or death (e.g., uterine rupture, admission to intensive care unit, septicemia)
- Neonatal infection, defined as culture proven sepsis, fever, or a suspicious clinical course that warranted treatment with antibiotics
- 5-minute APGAR score <7
- Umbilical artery acidemia ($\text{pH} < 7.0$ or base excess $> 12 \text{ mmol/L}$)
- NICU admission rate

- Composite neonatal outcomes (one of more of the following: perinatal death, severe respiratory distress requiring ventilation, neonatal encephalopathy, neonatal seizure, neonatal sepsis, 5-minute APGAR score <7, umbilical artery acidemia, NICU admission)
- Perinatal death

5. Criteria for Inclusion of Subjects:

- Women aged 18-50 years old
- Singleton gestation
- Nulliparous
- Vertex presentation
- Gestational age \geq 37 weeks
- No prior uterine surgery
- Presents for elective or medically indicated induction of labor
- Need for augmentation of labor with oxytocin

These inclusion criteria are a subset of the current inclusion criteria for low-dose and high-dose oxytocin use at our institution.

6. Criteria for Exclusion of Subjects:

- Previous cervical ripening using non-mechanical methods
- Patient unable or unwilling to provide verbal consent
- Contraindications to vaginal delivery
- Fetal demise or life-limiting anomaly
- Allergy to oxytocin
- Non-reassuring fetal heart tracing prior to inclusion
- Maternal pulmonary edema prior to inclusion
- Fetal growth restriction

7. Sources of Research Material:

Research material will be obtained from electronic medical records/charts.

8. Potential Risks:

No significant adverse effects are expected with the use of high-dose or low-dose oxytocin as both methods are the standard of care at UTMB. All enrolled subjects will meet the criteria for both low- and high-dose oxytocin protocols and will not be withheld standard of care as the result of randomization to either group. The most significant rare risks are described under section 8.3 below: uterine tachysystole, blood pressure changes, arrhythmias, and hyponatremia. The patient will undergo inpatient IOL or AOL, so any adverse reaction would be promptly detected and addressed.

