It is important to determine the optimal method for IOL and AOL, with the goal of the highest percentage of vaginal deliveries within the shortest period, with the lowest maternal and neonatal adverse outcomes. The optimal regimen would have the lowest exposure to all labor interventions. While low-dose oxytocin protocols may result in less uterine tachysystole and resulting fetal distress, studies have shown an increased length of labor, with associated increased rates of chorioamnionitis, fetal infection, and postpartum hemorrhage(11). Low-dose oxytocin protocols have also been associated with an increase in OVD for labor dystocia(10).

On the other hand, high-dose oxytocin has been associated with a shorter length of labor(5, 9, 10, 19) without an increase in cesarean delivery rates(5, 9, 11). It is also associated with lower incidences of postpartum hemorrhage and chorioamnionitis(9, 11). Though data is currently mixed, high-dose oxytocin protocols may be associated with decreased CD for labor dystocia(5), which would spare women from a major abdominal surgery. A shorter total labor duration would translate to a shorter overall hospital admission, ultimately decreasing overall utilization resources. This could then decrease medical costs for labor and delivery and optimize use of hospital staffing and resources. Thus, it is of benefit both patients and providers to further investigate the optimal methods for induction and augmentation of labor with oxytocin infusions based on evidence rather than physician preference.

13. Statistical analysis/Sample size:

Analysis will be performed by intention-to-treat. Univariable and multivariable analysis will be used to describe the population in the study and to identify potential confounding variables. For this analysis, normality will be tested using Shapiro-Wilk method. Demographics and descriptive statistics will be used to provide a profile of the study sample. Data will be either shown as median +/- IQR or mean +/- SDEV. Bivariate tests such as t test, Pearson's chi square, and

Mann-Whitney tests will be used as indicated to identify any key differences in the profiles of subjects across study conditions. Statistical analyses of primary and secondary outcomes between study groups will be performed by multilevel regression analysis accounting for both confounding variables as well as adjusting for any potential intra class correlation that may arise from the study design.

Sample size calculations

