Sample size was calculated based on the determination of superiority. The primary outcome is time in minutes from oxytocin initiation to delivery. For the sample size calculation, based on our prior unpublished data, the primary outcome in the low PIT arm would be 858.6 ± 494.9 mins. Using a difference rate of 25% (High Pit group: 643.9 mins), power of 80% and 2-sided alpha of 0.05,. Final sample size: 170 (85/group). This difference between both methods is clinically significant.

Detailed:

```
power twomeans 858.6 644, sd(494.9) power(0.8)
```

Performing iteration ...

Estimated sample sizes for a two-sample means test

t test assuming sd1 = sd2 = sd
H0: m2 = m1 versus Ha: m2 != m1

Study parameters:

```
alpha = 0.0500
power = 0.8000
delta = -214.6000
m1 = 858.6000
m2 = 644.0000
sd = 494.9000
```

Estimated sample sizes:

```
N = 170
N per group = 85
```

This trial will be registered with Clinical Trials Register (Clinicaltrials.gov) before recruitment is initiated and after IRB approval.

References

6. Obstetric care consensus no. 1: safe prevention of the primary cesarean delivery. *Obstet Gynecol.* 2014;123(3):693-711. doi: 10.1097/01.AOG.0000444441.04111.1d. PubMed PMID: 24553167.

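### Section 4.9 sets no onset rule for chorioamnionitis, so infection already present at randomization can count as an outcome and mildly dilute one unpowered secondary comparison

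*Combined protocol and SAP*

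**What the plan says.** **Outcome.** Section 4.9 lists chorioamnionitis as a secondary outcome. "A presumptive diagnosis can be made in women with" introduces a fever criterion plus one of three supporting signs: fetal baseline above 160, raised maternal white cell count, or purulent cervical fluid. A confirmed diagnosis needs all of that plus a laboratory or histopathologic finding. Neither level carries a start time. Endometritis, in the same list, does have a time window.

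**Eligibility.** Section 6 has eight exclusions. Two are tied to the time before enrollment: a non-reassuring fetal tracing and "Maternal pulmonary edema prior to inclusion". None names intra-amniotic infection or maternal fever, and Section 5 does not require their absence. Section 5 admits women needing augmentation, and Section 4.1 enrolls them once the team has decided that oxytocin is needed but before it is ordered.

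**Ascertainment and analysis.** Section 4.4 has maternal outcomes assessed after delivery and describes no infection status at baseline. Section 4.2 keeps every randomized woman in an intention-to-treat analysis.

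**Interest in the outcome.** Section 11 cites earlier work linking longer low-dose labor to "increased rates of chorioamnionitis, fetal infection, and postpartum hemorrhage".

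**The concern.** A woman needing augmentation may have been in labor for some time before she is randomized. If she already meets the Section 4.9 criteria, nothing in the listed exclusions names her condition and nothing in the definition sets her diagnosis aside. She then enters the comparison as a chorioamnionitis event whichever regimen she receives.

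Events fixed before allocation carry no information about the regimen. They add about the same amount to both arms, so they pull the risk ratio toward 1 and add noise. At stake is how clearly the trial can describe one of the infection outcomes that Section 11 mentions. The primary comparison of time to delivery is not at stake.

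**Working it through.** **1. The plan's own figure.** Section 13 gives "the primary outcome in the low PIT arm would be 858.6 ± 494.9 mins" and "power of 80% and 2-sided alpha of 0.05"; the software run uses 644.0 minutes for the high-dose arm.
- Difference: 858.6 − 644.0 = 214.6 minutes.
- Normal approximation: n per arm = 2 × (1.960 + 0.842)² × (494.9 / 214.6)² = 83.5, so 84.
- Two-sample t-test: 84.46, rounded up to 85 per arm, or 170 in total. The stated figure reproduces.

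This calculation uses only the primary outcome. The documents give no rate, effect size or power for chorioamnionitis, so nothing below changes 170.

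**2. Dilution formula.** Let q be the share of women who meet the criteria at randomization (equal in both arms in expectation) and r the new-onset risk among the rest.
- Observed risk = q + (1 − q) × r.
- Observed risk difference = (1 − q) × true risk difference.
- The observed risk ratio moves toward 1 as q rises.

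**3. Numbers.** All rates are assumptions: r = 15% low-dose and 10% high-dose, so the true risk ratio is 0.10 / 0.15 = 0.67 and the true difference 5.0 points.

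| q | Expected baseline cases in 170 | Low-dose observed | High-dose observed | Risk ratio | Difference (points) |
|---|---|---|---|---|---|
| 0% | 0 | 15.0% | 10.0% | 0.67 | 5.0 |
| 2% | 3.4 | 16.7% | 11.8% | 0.71 | 4.9 |
| 5% | 8.5 | 19.25% | 14.5% | 0.75 | 4.75 |
| 8% | 13.6 | 21.8% | 17.2% | 0.79 | 4.6 |

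Example at q = 5%: 0.05 + 0.95 × 0.15 = 0.1925; 0.05 + 0.95 × 0.10 = 0.145; ratio 0.145 / 0.1925 = 0.75; difference 0.95 × 5.0 = 4.75 points.

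**4. Other assumed rates.** With 10% against 5% (true ratio 0.50) and q = 5%, the ratio becomes 0.67 and the difference 4.75 points. With 20% against 10% and q = 5%, the ratio becomes 0.60 and the difference 9.5 points. The direction is the same throughout.

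**5. Power and precision at 85 per arm** (two-sided 0.05, normal approximation for two proportions, 15% against 10%). Power is about 16% with no baseline cases and about 13% at q = 5%. With those women removed (85 × 0.95 = 80.75 per arm) it is again about 16%. The approximate 95% interval for the risk ratio is 0.30 to 1.50 undiluted and 0.38 to 1.48 at q = 5%. The comparison is imprecise in every case.

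**The case against.** **The missing rule may exist elsewhere.** Section 4.9 is silent on onset; it does not say that earlier diagnoses count. Section 4.7 refers to a data collection sheet that is not among the documents and might already date the diagnosis. This stands as a limit on how firmly the point can be put. It does not remove the gap, because the definition as written is met by a diagnosis made before randomization.

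**Some of these women may never be enrolled.** The tracing exclusion could remove some, since a fetal baseline above 160 is one of the three supporting signs. It need not remove women who qualify by white cell count or purulent fluid. Section 3 also requires every woman to meet the institution's criteria for both oxytocin protocols, and those are not reproduced. So a reader should not infer that a woman with diagnosed infection is certainly eligible.

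**The risk ratio flatters the problem.** This stands. On the difference scale the loss is 0.1 to 0.4 points, and the outcome is unpowered with or without the change.

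**Chance imbalance.** A reader might infer that a few baseline cases falling unevenly under simple randomization could manufacture or hide a safety signal. That is ordinary chance error, which applies to every baseline factor and which the test and interval already reflect. It is not a separate defect of this definition.

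**Neonatal infection.** A reader might extend the dilution argument to "Neonatal infection, defined as culture proven sepsis, fever, or a suspicious clinical course that warranted treatment with antibiotics". It does not carry over. Maternal infection at randomization does not settle the newborn's outcome, because the interval to delivery, which the regimen is meant to shorten, still lies ahead. The neonatal event remains a post-randomization outcome.

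**Conclusion.** The point holds as a minor one. The definition lacks an onset rule, the listed exclusions do not fill the gap, and enrollment during labor makes baseline cases possible. Under the assumed rates (15% against 10% new onset, 2% to 8% at baseline), the risk ratio shifts from 0.67 to between 0.71 and 0.79 and the difference from 5.0 to between 4.9 and 4.6 points. The direction follows from the formula, given equal expected baseline shares and counting every baseline case as an event. The size rests wholly on assumption.

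The effect is dilution, not systematic bias in favor of either arm. No conclusion about the primary outcome depends on it. Section 11 presents chorioamnionitis as one association among several from earlier studies, and the plan states no hypothesis for it, so it should not be read as a principal claim of the trial.

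**What to change.** - Keep every randomized woman in the trial and in the primary intention-to-treat analysis.
- Record from the chart whether the clinical criteria in Section 4.9 (fever plus a supporting sign) were already met at randomization.
- Add to Section 4.9 that chorioamnionitis counts only when those clinical criteria are first completed after randomization. This also settles cases in which two qualifying temperatures fall on either side of randomization.
- Use histopathology to confirm a diagnosis but not to date it, since the placenta is examined only after delivery.
- Leave women positive at baseline out of the denominator for this outcome only, and report the all-women result as a sensitivity analysis. Baseline status is fixed before allocation, so this keeps the randomized comparison intact.

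An outcome rule is safer here than a new, undated exclusion. Section 4.6 withdraws women who meet an exclusion criterion and stops their data collection, so such an exclusion could delete genuine post-randomization events.

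**Cost.** One dated abstraction field, if the data sheet does not already have it; a short addition to Section 4.9; and a slightly smaller denominator for one secondary outcome.

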Different oxytocin dosing protocols have been studied in induction and AOL. One recent study studying the effect of oxytocin dosing in the augmentation of labor at one institution in the United States showed a reduction of primary cesarean delivery with high-dose oxytocin without an increase in obstetric or neonatal morbidity(9). A similar Swedish study showed no significant change in cesarean delivery rates(10). In that study and a systematic review of oxytocin dosing protocols for AOL, while high-dose oxytocin did increase the incidence of uterine tachysystole, this did not translate to an increase in CD for fetal distress (5, 10). Similar outcomes were seen for the induction of labor. An Australian study showed no change in cesarean or operative vaginal delivery (OVD) with different oxytocin dosing(11). A Cochrane review, including 9 studies, showed no significant difference in the mode of delivery, severe maternal morbidity, and

uterine hyperstimulation resulting in fetal distress with different oxytocin dosing(12). A significant limitation of these studies, however, includes patient homogeneity. While there is more research regarding optimal dosing for AOL, such information is sparse for labor induction.

Currently, at our institution, there is a similar lack of data regarding optimal oxytocin dosing. A change to our standard of care for oxytocin administration for augmentation of labor was introduced at the beginning of 2022, based on data from a randomized control trial performed at another institution (9). Under this new protocol, patients who meet criteria are eligible for either low-dose or high-dose oxytocin. The decision on which protocol to use is based mostly on provider preference while both dosing protocols are considered standard of care. While the safety of high-dose oxytocin has been previously established (5, 9-12), familiarity with low-dose oxytocin leads most providers to choose the low-dose protocol even when patients qualify for high-dose oxytocin. Thus, this study is crucial to further demonstrate the efficacy of high-dose oxytocin in our patient population and provide evidence to guide providers' decision-making regarding oxytocin dosing.

3. Concise Summary of Project:

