4.4 Additional Baseline Procedures

- Routine intrapartum care will be provided by the patient's managing obstetric team.
- A trained and experienced study team will be responsible for all research data abstraction.
- Maternal outcomes will be assessed following delivery.
- The PI and faculty sponsor will review and validate the diagnosis for all subjects identified to have the primary outcomes. If there is uncertainty, a faculty sponsor will review the chart, discuss with the study team, and make a final determination regarding the outcome.
- Data collection forms will be used during these processes and charts will be reviewed up to 30 days postpartum. We will collect demographic data, as well as data related to the patient's intrapartum course, delivery, immediate postpartum period while inpatient, and neonatal outcomes while inpatient.
- Subject's participation will end following delivery.

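### Endometritis is anchored to an undefined operative procedure, so read literally a woman with a spontaneous vaginal birth and no procedure can never be a case

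*Combined protocol and SAP*

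**What the plan says.** Section 4.9 introduces the outcome with "Endometritis: must meet the following criteria" and joins three criteria by AND:

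1. Timing: "Infection occurs within 30 days after the operative procedure AND"
2. The uterus is presumed to be involved.
3. Evidence, at least one of three items: purulent drainage from a surgically placed drain; "Organisms isolated from an aseptically obtained culture of fluid or tissue in the organ/space"; or "An abscess or other evidence of infection involving the abdomen or pelvis that is found on direct examination", with re-operation and histopathology as further routes to the last item.

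The term in the timing criterion appears nowhere else in the document, and no section says whether it means cesarean, operative vaginal delivery or something else.

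Other sections describe a trial of all births:

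- Section 4.1 enrolls women before oxytocin is ordered, so before mode of delivery is known.
- Section 6 excludes women with contraindications to vaginal delivery.
- Sections 4.2 and 13 specify intention-to-treat analysis.
- Section 4.4 says "Maternal outcomes will be assessed following delivery" and "charts will be reviewed up to 30 days postpartum", with no limit by mode. It also says that postpartum data are collected for the inpatient stay.
- Section 4.9 lists mode of delivery as a separate secondary outcome.

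**The concern.** The timing criterion is necessary for a case. A woman with a spontaneous vaginal birth and no procedure has no date from which its 30 days can run, so she counts as a non-case even with a positive aseptic culture. She still stays in the denominator.

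Two things follow. First, uterine infection after such births goes uncounted in both arms. Second, whether a woman can be a case depends on how she delivered, which happens after randomization and which dose may influence. The protocol's own sources leave that influence open. Section 2 cites one trial with fewer primary cesareans on high dose and another with no significant change. Section 11 cites more operative vaginal delivery for dystocia on low dose. If mode rates differ by arm, a rule confined to operative births carries that difference into the endometritis comparison more fully than a rule covering all births.

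**Working it through.** **The plan's own figure.** The plan gives no number for endometritis. Its sample size does reproduce: a two-sample t test with difference 214.6 min, SD 494.9, two-sided alpha 0.05 and power 80% needs 84.46 per group, rounded up to 85, so 170 in total. The point below does not touch this.

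**Logic.** A case requires timing AND uterine involvement AND evidence. With no procedure, timing fails, so the woman is a non-case whatever the other two show. If 25% of women had an operative procedure (assumed), 170 × 0.25 ≈ 42 could be cases and about 128 could not.

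**Share of cases missed.** Every input except the 170 is an assumption, because the documents give no rates:

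- c = cesarean rate, 25% in both arms; only cesarean counts as the procedure
- pc = infection risk after cesarean, 5-10%
- pv = infection risk after vaginal birth, 1-3%
- k = how often the evidence criterion is met after vaginal birth, relative to cesarean (set to 1 after cesarean)

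Missed share = (1 − c)·pv·k / [c·pc + (1 − c)·pv·k]

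| k | pc 10%, pv 1% | pc 5%, pv 3% |
|---|---|---|
| 1 | 0.0075/0.0325 = 23% | 0.0225/0.0350 = 64% |
| 0.5 | 0.00375/0.02875 = 13% | 0.01125/0.02375 = 47% |
| 0.1 | 0.00075/0.02575 = 3% | 0.00225/0.01475 = 15% |

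In women, multiplying by 170 and keeping each pair of risks together:

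- k = 1: 1.3 missed of 5.5, or 3.8 of 6.0
- k = 0.1: 0.1 of 4.4, or 0.4 of 2.5

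These totals are upper bounds under the assumed risks, because capture after cesarean is set to 1.

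**Other settings.** With cesarean at 20-30%, the range is 19-71% for k = 1 and 10-55% for k = 0.5. If 5-10% operative vaginal births also count as operative (c = 25%, k = 1), it is 20-60%, from (0.75 − v)·pv / (0.25·pc + 0.75·pv) with v = 0.05 or 0.10.

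**Ratio between arms, equal mode rates.** With equal risks by arm, the rule as written gives c·pc / c·pc = 1.00. Cases are lost but the ratio does not move.

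**Ratio between arms, unequal mode rates.** Suppose 20% cesarean in one arm and 30% in the other, with the same infection risk within each mode.

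- As written: 0.20/0.30 = 0.67
- All births, k = 1: 0.028/0.037 = 0.76 (10%/1%) to 0.034/0.036 = 0.94 (5%/3%)
- All births, k = 0.1: 0.0208/0.0307 = 0.68 to 0.0124/0.0171 = 0.73

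The delivery-anchored ratio also departs from 1. The wording enlarges the dependence on mode; it does not create it. In cases, at a 7.5% risk after cesarean, the as-written difference is 85 × (0.30 − 0.20) × 0.075 ≈ 0.6.

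**The case against.** **A deliberate post-operative outcome.** The drain, the re-operation wording and the timing anchor all sound surgical, so the definition may itself be the limit. That reading is possible, but the outcome would then carry a label broader than its rule, and a denominator that includes women who cannot be cases. It would still need editing.

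**Procedure may simply mean delivery.** The 30 days in the definition match the 30-day chart review, and the data collection sheet mentioned in section 4.7 is not available to settle the matter. But section 4.4 counts its window from birth in other words, and nothing tells an abstractor to treat the two as the same. In an unblinded trial with outcomes abstracted from charts, the rule should not be left to individual reading.

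**The amount lost may be small.** This stands. All the rates are assumed. The evidence criterion asks for culture, drainage, abscess, direct-examination or histopathologic findings, which may rarely be documented after vaginal birth. If so, the share lost falls to the 3-15% row.

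**Re-anchoring alone may not recover the cases.** This stands too. Section 4.4 limits postpartum data collection to the inpatient stay and ends participation after delivery, and section 4.5 plans no extra visits. A reader might infer from the 30-day review that no further data work is needed; the documents do not support that.

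**Conclusion.** The definition as written gives a wrong result for births without a procedure: it excludes them from ever being cases while no section excludes them from the outcome or its denominator. The consequence is under-ascertainment in both arms and a stronger dependence on mode of delivery than a delivery-anchored definition would have.

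The size is unknown. Under the assumed risks and 25% cesarean, about 3% to 64% of cases are missed, which is between a fraction of one woman and about four women in 170.

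Three stronger readings are tempting and are not supported:

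- A reader might infer that the comparison between arms is biased. That requires mode rates to differ by arm, which the documents leave open; with equal rates and equal risks the ratio stays at 1.00.
- A reader might infer a breach of intention-to-treat. All randomized women remain in their assigned groups; the fault lies in the case rule.
- A reader might infer that most infections are lost. Only some of the assumed settings give more than half.

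This is a minor correction to one secondary outcome. The primary outcome and N = 170 are unaffected.

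**What to change.** Replace the timing criterion with *within 30 days after delivery (any mode)*. Keep the culture, direct-examination and histopathology items, which can be met after vaginal birth. State in section 4.4 that the 30-day chart review, and not the inpatient limit, governs this outcome.

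If an operative-only outcome is intended, rename it (for example, *post-operative uterine infection*), list the procedures that count, and match the denominator to the women who had one.

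The cost is a short definition edit plus, for the first option, abstraction of post-discharge chart entries within the 30-day review already planned. The sample size and primary analysis do not change.

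### The endometritis definition in Section 4.9 has no clinical tier, so a charted, antibiotic-treated case without drain, culture or examination evidence is scored as absent (minor; cheap to fix).

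*Combined protocol and SAP*

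**What the plan says.** Section 4.9 opens the definition with "Endometritis: must meet the following criteria" and then joins three limbs by AND:

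1. Timing: "Infection occurs within 30 days after the operative procedure AND".
2. Site: "Infection presumed to involve the uterus AND".
3. Confirmation: "Patient has at least one of the following", followed by three items:
   - (a) "Purulent drainage from a drain that is placed through a stab wound into the abdomen or pelvis";
   - (b) "Organisms isolated from an aseptically obtained culture of fluid or tissue in the organ/space";
   - (c) an abscess or other evidence of abdominal or pelvic infection, found on direct examination, at re-operation or by histopathology.

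Direct examination is not defined. Fever, a clinician's diagnosis and antibiotic treatment do not appear in the list.

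The other two infections defined in Section 4.9 are handled differently. Chorioamnionitis has a presumptive tier (fever plus one further sign) and a confirmed tier that adds laboratory or histologic findings. Neonatal infection can be met by "a suspicious clinical course that warranted treatment with antibiotics".

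On data sources, Section 7 states: "Research material will be obtained from electronic medical records/charts". Section 4.4 extends chart review to 30 days after birth and plans validation of the diagnosis for the primary outcomes only.

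**The concern.** Items (a) to (c) read like criteria for a deep surgical-site infection. Because the limbs are joined by AND, presumed uterine infection is not enough. For endometritis alone in this section, evidence of the confirmatory kind is the entry requirement, where for chorioamnionitis it only upgrades a case.

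No study procedure obtains cultures or tissue, so qualifying evidence exists only where routine care happened to produce and chart it. No stated adjudication step would let a clinically clear case count.

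At stake is under-ascertainment of a listed maternal safety outcome. Section 11 uses infection in its benefit argument, linking longer labor under low-dose regimens to more infection. A maternal infection outcome that misses treated cases is poorly placed to show either harm or benefit.

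**Working it through.** **The plan's own figure.** The plan gives no number for endometritis. The only plan figure used here is the sample size, and it reproduces. With a difference of 214.6 min, SD 494.9, two-sided alpha 0.05 and power 80%, the normal approximation gives 2 × (1.960 + 0.842)² × (494.9/214.6)² = 83.5, so 84 per arm. The t-test version gives 84.46, so 85 per arm and 170 in total, as stated in Section 13. That calculation is for the primary outcome and does not depend on this definition.

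**Reading the rule.** Scored case = limb 1 AND limb 2 AND (a OR b OR c). Take a woman with a charted diagnosis, antibiotics and recovery.

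- No drain: (a) fails.
- No positive aseptic culture: (b) fails.
- No finding on direct examination, re-operation or histopathology: (c) fails.

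Limb 3 fails, and she is a non-case whatever the mode of delivery. If her examination showed uterine tenderness or purulent discharge, the answer turns on whether that is other evidence found on direct examination. The text does not settle this.

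Limb 1 acts separately. Read literally, a birth with no operation has no operative procedure from which to count 30 days, so it fails before limb 3 is reached, even with a positive culture.

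**Size, on assumptions only.** Let p be the incidence of clinical endometritis and s the share with qualifying evidence. Neither is in the documents. Limb 1 is taken as corrected. Expected counted cases = 170 × p × s; chance of none = (1 − p × s)^170.

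| p | s = 10% | s = 30% | s = 70% |
|---|---|---|---|
| 2% | 0.34 cases; 71% | 1.02; 36% | 2.38; 9% |
| 3% | 0.51; 60% | 1.53; 22% | 3.57; 3% |
| 5% | 0.85; 43% | 2.55; 8% | 5.95; 0.2% |

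Worked examples at p = 3%: (1 − 0.003)^170 = 0.600 with s = 10%; (1 − 0.021)^170 = 0.027 with s = 70%. The 10% and 30% columns correspond to a narrow reading of direct examination, and the 70% column to a reading that admits bedside findings.

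**Power with full capture.** For assumed rates of 5% and 2% with 85 per arm, expected cases are 85 × 0.05 = 4.25 and 85 × 0.02 = 1.70. A two-sided 0.05 comparison of proportions has power of about 18%.

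**The case against.** The strongest reply has four parts.

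**Item (c) may be wider than it looks.** It speaks of other evidence that is found, and lists direct examination apart from re-operation, so it need not mean surgical exposure. On that reading many bedside diagnoses qualify. This stands, and it limits the claim. A reader might infer that the outcome only records how often clinicians cultured or re-operated. The documents do not support that, because direct examination requires neither and charts may hold cultures and pathology ordered in routine care. Against the wide reading, the chorioamnionitis definition names its bedside signs explicitly, which the endometritis definition does not do. The wording is unresolved, and two abstractors could score one chart differently.

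**Objective criteria are defensible in an open-label trial.** Section 4.2 says blinding is not possible, and a charted diagnosis with antibiotics reflects the judgement of clinicians who know the allocation. This stands as a reason to keep the objective criteria. It does not require leaving clinical cases unreported.

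**The inferential loss is small.** Power is low under any definition, and chorioamnionitis and septicemia are recorded as well. This stands. A reader might also expect a near-zero count to be presented as evidence of no excess infection; no part of the plan says so.

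**The time anchor does more damage after births without an operation.** This also stands. While limb 1 is read literally, limb 3 makes a difference only after operative births, so the two belong in one edit.

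**Conclusion.** The point holds as a cheap improvement of minor severity. As written, limb 3 scores a charted, antibiotic-treated endometritis as absent when there is no drain pus, positive culture or examination evidence, and the section's other defined infections are not treated this way. That follows from the text without any assumption.

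The number of cases lost cannot be fixed from the documents. At an assumed 3% incidence, the chance that the whole trial counts no case is about 60% if 10% qualify and about 3% if 70% qualify. It would be wrong to quote the upper figure alone, since it presupposes the narrow reading of direct examination.

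It is tempting to go further and say that every clinically diagnosed case is lost, or that detection will differ between arms because drains and re-operation presuppose surgery. The first fails if bedside findings count. The second is possible, but nothing in the documents gives its direction or size.

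The primary outcome and the sample size of 170 are unaffected.

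**What to change.** In Section 4.9, for outcome scoring only and with no change to care:

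1. State what direct examination includes, in particular whether uterine tenderness or purulent discharge at the bedside counts.
2. Add a clinical tier: a charted diagnosis of endometritis treated with antibiotics, with no other identified source of infection.
3. Keep the present objective criteria and report them as the confirmed subset, following the two-tier layout used for chorioamnionitis.
4. Correct the operative-procedure time anchor in the same edit, so that timing also applies to births with no operation. Without this, the new tier has no effect after those births.
5. Report both tiers by arm.

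**Cost.** A few lines in Section 4.9 and probably one field on the data collection form. That form is not among the documents, so it may already capture the diagnosis. No new test or visit is needed, because charts are already reviewed to 30 days after birth.

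**Downside.** The clinical tier is less specific and, with treatment unblinded, open to clinician judgement. Showing the confirmed subset beside it lets the reader see whether any difference between arms rests on judgement alone.
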